## **2 Statistical methods**

### **2.1 Data analysis general information**

The statistical analysis will be performed by Novartis. The most recent version of SAS® (SAS Institute Inc., Cary, NC, USA) available in the statistical programming environment of Novartis will be used for the analysis.

#### **2.1.1 General definitions**

In this document, although investigational treatment is given in addition to background standard of care therapy, ‘study medication’, ‘study treatment’ or ‘study drug’ will be used to refer to investigational therapy assigned to a patient. Specifically, for the double-blind treatment period, study treatment refers to QAW039 or placebo as assigned to a patient at randomization.

The date of the first administration of the investigational treatment (QAW039 or matching placebo) is referred to as the date of first administration of study treatment in the study. The evaluations which have complete date and time values are assigned to pre or post-dose assessment based on the actual date/time. However, evaluations with missing date/time are assigned to their respective scheduled visit date and time given the visit number and time point are non-missing. If an evaluation scheduled as pre-dose is actually performed post-dose, or vice

versa, the data will not be used for inferential analysis and summary statistics but will be included in the summaries of the notable values and extreme values.

Study day will be defined as the number of days since the date of first dose of study medication. The date of first dose of study medication will be defined as Day 1 and the day before the first dose of study medication is defined as Day -1.

Therefore, for a particular date, study day will be calculated as follows:

- for dates on or after the first date of study medication,  
Study day = Assessment date – Date of first dose of study medication + 1;
- for dates prior to the first date of study medication,  
Study day = Assessment date – Date of first dose of study medication.

If a patient never took any study medication, the randomization date will be used instead of the date of first dose of study medication. In this case, the randomization date is defined as Day 1 and the day prior to randomization is defined as Day -1.

#### 2.1.1.1 Baseline definition

Data from unplanned visits prior to screening are not included in analysis. In general, baseline is defined as the last assessment taken prior to the first dose of study drug at Day 1 (Visit 201).

Checks will be performed to ensure the assessments were taken prior to the first dose of study drug on Day 1 (Visit 201). If the assessment is missing or not confirmed to be pre-dose, then the last available non-missing assessment will be used as baseline. Missing baseline pre-dose FEV1, daytime asthma symptoms, total daily SABA use and AQLQ+12 will be assumed to be missing at random as assessments are performed prior to any knowledge of treatment allocation and will be imputed using the mean value of all randomized patients.

**Table 2-1 Baseline definition of analysis parameters**

Parameter	Baseline assessment	Detail
ACQ-5, AQLQ [REDACTED]	Last assessment prior to the first dose of study drug on Day 1	If the Day 1 assessment is missing the last available assessment (scheduled or unscheduled) taken prior to the first dose of study drug will be used.

Lung function (FEV 1 )	Average of the two FEV 1 assessments taken at 45 minutes and 15 minutes prior to the first dose of study drug on Day 1	Checks will be performed to ensure both values were taken prior to the first dose of study drug. If one of the 45 and 15 min values is missing (or is not confirmed to be pre-dose) then the remaining non-missing value will be taken as the baseline. If both assessments are missing (or are not confirmed to be pre-dose) then the last available FEV 1 measurement (scheduled or unscheduled) prior to Day 1 will be used for baseline.
eDiary data (Daytime asthma symptoms)	Average of the mean daytime asthma symptom score from Visit 101 to Day 1	The baseline score will be calculated as long as there are at least 4 days with non-missing eDiary data. Noted that the morning assessment for Day 1 counts towards the baseline.
eDiary data (Total daily use of SABA)	Average of total daily SABA use from Visit 101 to Day 1	The baseline score will be calculated as long as at least 4 days with non-missing eDiary data. Noted that the morning assessment for Day 1 counts towards the baseline while the evening assessment for Day 1 counts as the treatment period.

Laboratory data (hematology, clinical chemistry, urine analysis)	Last available assessment (scheduled or unscheduled) prior to dosing on Day 1	
Vital signs (pulse rate and systolic & diastolic blood pressures)	Last available assessment (scheduled or unscheduled) prior to dosing on Day 1	
Height and weight	Last available assessment (scheduled or unscheduled) prior to dosing on Day 1	
ECG	Last available assessment (scheduled or unscheduled) prior to dosing on Day 1	

### 2.1.1.2 Post-baseline measurement

Post-baseline measurements are defined as those assessments after the start of the study treatment.

When change from baseline is of interest, the following formula will be used for each visit and time-point where baseline and post-baseline values are both available:

Change from baseline = post baseline value – baseline value.

## 2.2 Analysis sets

The following analysis sets are defined:

- The screened set (SCR) will include all patients who provided informed consent.
- The randomized (RAN) set will consist of all patients who were assigned a randomization number, regardless of whether or not they actually received study medication. Patients in RAN will be analyzed according to the treatment they were randomized to.
- The Full Analysis Set (FAS) will consist of all randomized patients who received at least one dose of study medication. It was considered reasonable to limit the FAS to patients who took trial medication, because the decision on whether or not study drug is started will not be influenced by the treatment group assignment due to the effective treatment blinding procedures. Following the intent-to-treat principle, patients will be analyzed according to the treatment they were assigned to at randomization. The FAS will be used for the analysis of all efficacy endpoints, and for the summaries of patient disposition, demographic and baseline characteristics.
- The Per-Protocol Set (PPS) will include all patients in the FAS who did not have any major protocol deviations such as violation of major entry criteria. Protocol deviations will be defined in the data review plan document prior to database lock and the un-blinding of the study. Protocol deviations leading to exclusion from analysis sets are

## 2.3 Patient disposition, demographics and other baseline characteristics

### 2.3.1 Patient disposition

The number of patients screened, randomized, completed and discontinued from the study will be summarized for each study phase (i.e., screening, run-in, and treatment). In addition, the number of patients randomized, completed and discontinued from the 12-week treatment period will be summarized by country. Screened set and its subset of patients who received placebo study medication during the run-in period will be used for screening period and run-in period disposition tables, respectively. RAN will be used for treatment disposition outputs. Patients discontinued from the 12-week treatment period will also be summarized with reasons for discontinuation. Patients who discontinued study treatment but stayed in the study will be considered as completing the 12-week treatment period. Patients who discontinued study treatment but stay in the study are defined as patients with the date of study discontinuation or Visit 299 - the end date of study treatment > 0. Patient randomization numbers and whether they completed or discontinued from the study will be listed, with date of last dose and primary reason for discontinuation, including the unblinding date if applicable. Rescreening information will also be summarized mentioning the number of patients who were rescreened and how many of them were randomized.

Time to study discontinuation will be displayed graphically for each treatment group using a Kaplan-Meier curve for the FAS. The date of study discontinuation is defined as the maximum of the last known visit date for treatment period and the date of last dose of study medication. Patients who completed the study will be censored at the final study visit.

Number of patients with protocol deviations and protocol deviations that lead to exclusion from analysis sets will be tabulated by deviation category and treatment group for the RAN.

The number of patients included in each analysis set will be tabulated by treatment group for the RAN. Reasons for exclusions from analysis sets will be tabulated. Patient exclusion from analysis sets will be listed for all patients with reasons for exclusion (including protocol deviations).

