- If a patient develops a medical condition that requires consistent use of prohibited treatment as per [Section 5.5.8](#) or if patient exhibits a behavior of non-compliance regarding prohibited medication.

If discontinuation of study treatment occurs, the patient should NOT be considered withdrawn from the study. The patient should return to the clinic as soon as possible, after discontinuation of study drug, for a study treatment discontinuation visit. Treatment discontinuation visit assessments detailed in the "treatment discontinuation visit" (TD) in [Table 6-1](#) should be completed and recorded in the eCRF. The investigator must determine the primary reason for the patient's premature discontinuation of study treatment and record this information on the dosage administration record eCRF.

The investigator and study staff must discuss with the patient his/her continued participation in the study and request he/she continues attending study visits according to the study visit schedule with all assessments completed up to Visit 299. If the patient cannot or is unwilling to attend any further visit(s), the site staff should maintain regular phone contact with the patient, or with a person pre-designated by the patient. This phone contact should preferably be done according to the study visit schedule.

After study drug discontinuation, at a minimum, in abbreviated visits, the following data should to be collected at clinic visits or via telephone visits:

- new / concomitant treatments
- adverse events/Serious Adverse Events (SAE)

The investigator must also contact the IRT to register the patient's discontinuation from study drug.

If study drug discontinuation occurs because treatment code has been broken, please refer to [Section 5.5.9](#).

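### The rule in SAP 2.3.1 can count patients who stopped study drug and then left the study as completers of the 12-week period

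*SAP*

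**What the plan says.** SAP 2.3.1 tabulates patients who completed and who discontinued the treatment period, overall and by country, on the randomized set. Patients who stopped study drug but remained in the study "will be considered as completing the 12-week treatment period". The operational definition follows: "Patients who discontinued study treatment but stay in the study are defined as patients with the date of study discontinuation or Visit 299" minus the end date of study treatment, greater than zero. Later in the section: "The date of study discontinuation is defined as the maximum of the last known visit date for treatment period and the date of last dose".

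Two other outputs in SAP 2.3.1 bear on this. One is a table of reasons: "Patients discontinued from the 12-week treatment period will also be summarized with reasons for discontinuation". The other is a patient listing, which shows "whether they completed or discontinued from the study will be listed, with date of last dose and primary reason for discontinuation".

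Protocol 5.6.2 describes what happens when drug is stopped: "The patient should return to the clinic as soon as possible, after discontinuation of study drug, for a study treatment discontinuation visit". The site then asks that the patient "continues attending study visits according to the study visit schedule with all assessments completed up to Visit 299". If the patient cannot or will not attend, the site keeps up telephone contact, and as a minimum "the following data should to be collected at clinic visits or via telephone visits": new or concomitant treatments and adverse events.

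**The concern.** Crediting patients who stop drug but complete follow-up is sound. The date rule does not implement that aim. It asks only whether something happened after the last dose, not whether the patient reached Week 12. It also accepts a date of study discontinuation as evidence that the patient did not discontinue.

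The trigger is the pathway the protocol itself requests. Everyone who stops drug is asked back for a treatment discontinuation visit, and Protocol Table 6-1 places that visit in the treatment period with no witnessed dose. A patient who leaves at that visit, a day or more after the last dose, passes the test.

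At stake are the overall and by-country completion counts and the table of reasons for discontinuing the period, from which these patients would drop out. Readers use these tables to judge retention and how much outcome data may be missing.

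**Working it through.** The documents state no completion figure, so there is none to reproduce. The check applies the rule as written and then bounds its effect with the plan's own assumptions.

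**The rule.** Let L be the day of the last dose and V the day of the last treatment-period visit. The date of study discontinuation is D = max(V, L). A leaver has no Visit 299, so the test is D − L > 0, which reduces to V > L.

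| Patient who stopped drug | D − L | By the rule | Reached Visit 299 |
|---|---|---|---|
| Last dose Day 1, discontinuation visit Day 2, leaves | max(2, 1) − 1 = 1 | completer | no (84 − 2 = 82 days left) |
| Last dose Day 28, discontinuation visit Day 30, leaves | max(30, 28) − 28 = 2 | completer | no |
| Last dose Day 20, Week 4 visit Day 28, leaves | max(28, 20) − 20 = 8 | completer | no |
| Last dose Day 20, discontinuation visit the same day, leaves | max(20, 20) − 20 = 0 | discontinued | no |
| Last visit Day 28, last dose Day 40, no further visit | max(28, 40) − 40 = 0 | discontinued | no |
| Last dose Day 20, attends Visit 299 on Day 84 | 84 − 20 = 64 | completer | yes |

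Among leavers, the rule separates those with a visit after the last dose from those without one. It does not separate patients who stayed 12 weeks from those who left.

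**Inputs for size.** 650 patients, 325 per arm, and 15% stopping drug (SAP 3; Protocol 9.8). Half of those who stop complete the trial (footnote to SAP Table 3-2). The 20% discontinuation scenario comes from SAP Table 3-1; applying the same half to it is an assumption here.

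- Patients stopping drug: 650 × 0.15 = 97.5.
- Of these, not completing the trial: 97.5 × 0.5 = 48.75, which is 48.75 / 650 = 7.5%, or 325 × 0.15 × 0.5 = 24.4 per arm.
- Correct completion: 100% − 7.5% = 92.5%.
- In the 20% scenario: 650 × 0.20 × 0.5 = 65 leavers (10%), correct completion 90%.

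Let s be the share of leavers with V > L. The documents do not give it, so the full range is shown. Reported completion = 100% − 7.5% × (1 − s), with 10% in place of 7.5% in the second scenario.

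| s (assumed) | 15% stop drug | 20% stop drug |
|---|---|---|
| 0 | 92.5% | 90% |
| 0.5 | 96.25% | 95% |
| 0.9 | 99.25% | 99% |
| 1 | 100% | 100% |

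**The case against.** Several points can be made for the plan.

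- **The upper end is unlikely.** Patients who simply stop attending usually have their last dose on or after their last visit, because doses are witnessed at clinic visits. Their difference is 0 and they are correctly counted as discontinued. This stands: 100% is a bound, not an expectation.
- **Telephone follow-up is provided for.** Protocol 5.6.2 allows participation to continue without clinic attendance, so some of the 49 may not have left at all. This stands too. It lowers the upper bound by their number and means they need a category of their own.
- **The definition of the discontinuation date sits in the Kaplan-Meier paragraph.** Using it in the disposition rule is an inference. It makes little difference, because any recorded discontinuation date after the last dose gives the same result.
- **Visit remapping in SAP 6.3 might help.** It assigns a discontinuation visit to Week 12 only if Visit 299 was missed and Day 84 is the nearest planned day. Earlier leavers are untouched, and the disposition rule does not refer to remapping.
- **Other outputs show part of the picture.** The listing gives individual status, last dose and reason. SAP 2.4.1 reports treatment discontinuation with reasons and a Kaplan-Meier curve, and SAP 2.3.1 also plans a curve of time to study discontinuation. These limit the harm, but none corrects the overall, by-country or reasons tables.

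**Conclusion.** The rule as written misclassifies any patient who stopped drug and then left if a treatment-period visit falls a day or more after the last dose. Nothing elsewhere in the documents overrides it for these tables. The possible overstatement is 0 to 7.5 percentage points (0 to about 49 of 650 patients), or 0 to 10 points (0 to 65 patients) in the 20% scenario. The bounds rest on the plan's discontinuation assumptions and on treating everyone who does not complete the trial as having left. The actual number cannot be derived, because visit timing after the last dose is not given.

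The effect is confined to descriptive disposition outputs; the primary analysis does not use the rule. One caution: the rank-based analysis in SAP 2.5.5 places trial completers above withdrawals without saying how completion is derived. Reusing this flag there would rank some leavers too high, but the SAP does not say that it is reused. The defect in the wording is clear and should be corrected; its practical size is uncertain.

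**What to change.** In SAP 2.3.1, replace the date-difference rule as follows.

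- A patient who stopped study treatment counts as completing the 12-week period only if Visit 299 was attended.
- A patient followed only by telephone to Week 12 is shown in a separate category, neither completer nor discontinued. The SAP should say how such patients are dated in the curve of time to study discontinuation, since the existing date would place their departure at the last clinic visit or last dose.
- All others who stopped treatment count as discontinued from the period, appear in the reasons table, and keep the SAP's existing date of study discontinuation.

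The text should also state that a discontinuation visit remapped to Week 12 under SAP 6.3 is not by itself attendance at Visit 299 for disposition.

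The cost is a change of SAP wording and one derivation. Visit 299 attendance is already recorded and Protocol 5.6.2 already asks for the telephone contacts, so no new data are needed.

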### 2.3.2 Patient demographics and baseline characteristics

Demographics and baseline characteristics will be summarized by treatment group using the FAS set. Summaries will include age, gender, race, ethnicity, height, weight, BMI, pre- and post-bronchodilator FEV1, percent predicted FEV1, [REDACTED] FEV1 reversibility, duration of asthma, number of asthma exacerbations in prior year, atopic asthma at entry into the study (Yes/No), smoking history (never/former), number of pack years, baseline ACQ-5, baseline AQLQ+12, [REDACTED], and ICS use (alone, plus LABA, plus LTRA), , ICS dose ranges (low, medium, high), [REDACTED] and daytime asthma symptom scores.

Background asthma therapy will be categorized into GINA steps and will be summarized at baseline. Background asthma therapy is defined as concomitant medication start date on or before Visit 1 and end date after Visit 1. Continuous variables will be summarized using

descriptive statistics (number of non-missing data, mean, standard deviation, median, first and third quartiles, minimum, and maximum) and categorical variables will be summarized in terms of the number and percentage of patients in each category including a category for missing data if any for the treatment group.

No statistical analyses will be provided for baseline comparability among the treatment groups.

In addition, the following categorizations of continuous variables will be done:

- Age: <18, 18 to <65, and  $\geq 65$  years;
- BMI:  $\leq 30.0 \text{ kg/m}^2$  and  $> 30.0 \text{ kg/m}^2$ ;
- Duration of asthma: < 1 year, 1 - 5 years, > 5 - 10 years, > 10 - 15 years, > 15 - 20 years, and > 20 years;
- Number of asthma exacerbations in prior year: 0, 1-2, 3, 4,  $\geq 5$
- pre-bronchodilator percent predicted FEV1:  $\leq 40\%$ ,  $>40\% - \leq 50\%$ ,  $>50\% - \leq 60\%$ ,  $>60\% - \leq 70\%$ ,  $>70\% - \leq 80\%$ ,  $>80\%$
- ACQ-5: 1.5- < 2, 2 - < 2.5,  $\geq 2.5$  (< 1.5 will be added in case of protocol deviations)

### **Derivation of the demographics and baseline characteristics**

- BMI is calculated as:  $\text{BMI (kg/m}^2\text{)} = \text{Weight (kg)} / [\text{Height (m)} * \text{Height (m)}]$
- Estimated number of pack years is calculated by the total years of smoking multiplied by cigarette packs smoked per day. This will be summarized as recorded on the eCRF. Smoking history in package years will be calculated as: (1 pack year = 20 cigarettes/day x 1 year or 10 cigarettes/day x 2 years).
- % of (pre-bronchodilator) predicted FEV1 is obtained as a percentage of FEV1 relative to the predicted normal value.
- FEV1 reversibility is calculated as percentage increase of FEV1 values after inhalation of bronchodilator relative to FEV1 values prior to the inhalation. At visits with two pre-dose spirometry assessments, the FEV1 from the 2nd pre-dose spirometry assessment (15 min prior to in-clinic witnessed study drug administration) should be considered the pre-bronchodilator FEV1 value. A patient is considered to have demonstrated reversibility at clinic at baseline if there is an increase of 12% and  $\geq 200$  ml any particular visit prior to Day 1.
- Duration of asthma is calculated from the date of asthma first diagnosed recorded on the eCRF until the 1st visit. If the date is missing in day and/or month, it will be imputed as follows. If the year is before the first visit, the missing days will be imputed as the first of the month and the missing months will be imputed as July. If the year is the current year of the first visit, the missing days will be imputed as the first of the month and the missing months will be imputed as January.

- The total daily ICS dose at baseline will be categorized as low, medium, high based on the Appendix 6 in study protocol.

### **2.3.3 Medical history**

Medical history will be coded with the Medical Dictionary for Regulatory Activities terminology (MedDRA) using the most recent version at the time of database lock. History/conditions as well as protocol solicited events for asthma will be summarized for the FAS set by primary system organ class and preferred term. Verbatim recorded history/conditions will be listed together with the coded terms, date of diagnosis/surgery and whether the problem was ongoing at start of the study.

## **2.4 Treatments (study treatment, rescue medication, concomitant therapies, compliance)**

### **2.4.1 Study treatment / compliance**

#### **2.4.1.1 Duration of exposure**

Duration of exposure to a treatment will be calculated as the number of days between the first dose date and the last dose date exposed to that treatment over the specified period (expressed as: Duration of exposure = Date of last known dose of study drug – Date of first dose of study drug + 1).

The duration of exposure will be summarized by treatment group for the safety set as a continuous variable with the standard descriptive statistics.

The number of patients who completed the 12-week study treatment and who discontinued prematurely will be shown including the reasons for discontinuation of study treatment. In addition, the duration of exposure will be summarized as a categorical variable classified into <4 weeks, >=4 to <12 weeks, >=12 weeks.

